## List of Abbreviations and Definition of Terms

Abbreviation	Definition
AE	Adverse event
IMP	Investigational medicinal product
MedDRA	Medical Dictionary for Regulatory Activities
TEAE	Treatment-emergent adverse event
descriptive statistics	number of subjects, mean, SD, minimum, median, and maximum
frequency distributions	number of subjects, %

## **1 Introduction**

This statistical analysis plan documents the details of the statistical analysis methodology to be applied in the protocol of Trial 156-102-00123.

## **2 Trial Objectives**

Primary: To determine the efficacy, safety, and dose and regimen of tolvaptan in pediatric heart failure patients with volume overload

Secondary: To determine the pharmacokinetics and pharmacodynamics of tolvaptan when administered to pediatric heart failure patients with volume overload

## **3 Trial Design**

### **3.1 Type/Design of Trial**

This is a multicenter, open-label, uncontrolled, dose-titration trial. In this trial, an ascending dose regimen where administration is started at a low dose is employed to ensure the safety of subjects. After completion of a screening examination, subjects will be hospitalized prior to the evening meal on 3 days before start of tolvaptan administration. Tolvaptan administration will be started at 0.05 mg/kg/day, and subjects with sufficient increase in urine volume will continue administration at 0.05 mg/kg/day for 3 days. For subjects whose urine volume does not sufficiently increase, the dose may be increased to 0.15, 0.3, or 0.5 mg/kg/day according to the specification. In that case, the dose should be decided for each individual subject to obtain sufficient increase in urine volume, and administration at the decided dose will be continued for 3 days. When the dose is increased to 0.5 mg/kg/day, administration at 0.5 mg/kg/day should be continued for 3 days. After final tolvaptan administration, subjects will continue to be hospitalized for 2 days to undergo monitoring of condition. Subjects will also undergo the follow-up 5 to 7 days after final tolvaptan administration.

### **3.2 Trial Treatments**

#### **3.2.1 Dose and Regimen**

Subjects will take tolvaptan 1% granules or tolvaptan 15-mg tablet with water once daily after breakfast.

The initial dose of tolvaptan will be 0.05 mg/kg/day. From the second day of the treatment period and onward, if necessary the dose may be increased to 0.15, 0.3, or 0.5 mg/kg/day according to the rules specified in [Section 3.2.2](#), and then the dose decided for each individual subject will be administered for 3 days. The dose of tolvaptan 1% granules to be administered will be determined depending on the subject's body weight on the day before start of tolvaptan administration; however, the maximum dose is 15 mg/day even if the calculated dose exceeds 15 mg/day. For administration at the maximum dose of 15 mg, tolvaptan 15-mg tablet may be administered in place of tolvaptan 1% granules. If the investigator or subinvestigator judges that there are an excessive aquaresis or safety concerns of subjects, the dose may be reduced (see [Section 3.2.3](#)). For subjects who need to continue treatment after 3-day administration at the dose decided individually, extended treatment for up to 4 days is allowed if the aim is to collect data on administration for up to 7 days and if the investigator or subinvestigator considers the safety of subjects to be ensured (including ensuring safety by dose reduction) (see [Section 3.2.4](#)). The dose, the date and time of administration, and the reason for dose reduction (for dose reduction, see [Section 3.2.3](#)) will be recorded in a source document and a case report form (CRF).

### **3.2.2 Increasing the Dose of Tolvaptan**

Tolvaptan should be administered according to the following procedure. Daily urine volume should be assessed as "insufficient increase in urine volume" when it is less than 150% of that for the pretreatment observation period (1 day before start of tolvaptan administration), and "sufficient increase in urine volume" when it is at least 150%.

- 1) Tolvaptan administration will be started at 0.05 mg/kg/day, and administration at 0.05 mg/kg/day will be continued for 2 days.
- 2) For subjects with sufficient increase in urine volume on Day 1 or Day 2 of treatment, administration at 0.05 mg/kg/day will be continued for 3 days. For subjects with an insufficient increase in urine volume on Day 1 and Day 2 of treatment, the dose will be increased to 0.15 mg/kg/day on Day 3.
- 3) If a sufficient increase in urine volume is observed following 2-day administration at 0.15 mg/kg/day on Day 3 or Day 4 of the treatment period, administration at 0.15 mg/kg/day will be continued for 3 days. For subjects with an insufficient increase in urine volume on Day 3 and Day 4 of the treatment period, the dose will be increased to 0.3 mg/kg/day on Day 5.
- 4) If a sufficient increase in urine volume is observed following 2-day administration at 0.3 mg/kg/day on Day 5 or Day 6 of the treatment period, administration at 0.3 mg/kg/day will be continued for 3 days. For subjects with an insufficient increase in urine volume on Day 5 and Day 6 of the treatment period, the dose

will be increased to 0.5 mg/kg/day on Day 7, and administration at 0.5 mg/kg/day will be continued for 3 days.

### **3.2.3 Reducing the Dose of Tolvaptan**

If symptoms associated with excessive aquaresis such as persistent sensation of thirst, dehydration, and hypernatremia are observed or there are safety concerns in subjects, at a discretion of the investigator or subinvestigator, the dose may be reduced only to the next lower dose. In that case, however, the dose of conventional diuretics should not be changed. If the dose of tolvaptan needs to be reduced before completion of 3-day administration at the same dose, it should be administered at the reduced dose for 3 days. If the dose of tolvaptan needs to be further reduced after dose reduction to the next lower dose, the subject will be judged to have a problem with tolerability to tolvaptan and should be withdrawn from the trial.

### **3.2.4 Extended Treatment With Tolvaptan**

If the investigator or subinvestigator judges that the safety of subjects can continue to be ensured (including ensuring safety by dose reduction) after 3-day administration at the dose decided according to the specification for increasing the dose of tolvaptan (see [Section 3.2.2](#)), administration at that dose may be continued for up to 4 days (for up to 7 days in total).

In the case of an extended treatment with tolvaptan at reduced dose, the total number of administration days should be up to 7 days, which consists of “the days of administration at the dose just before the dose requiring reduction,” “the days of administration at the dose requiring reduction” and “the days of administration at the dose reduced to the next lower dose.”

### **3.2.5 Treatment Period**

According to the patterns of treatment with tolvaptan, the duration of treatment period will be 3 days at the shortest, and 13 days at the longest if tolvaptan is administered until the dose is increased to 0.5 mg/kg/day, at 0.5 mg/kg/day for 3 days, and at 0.5 mg/kg/day for additional 4 days.

## **3.3 Trial Population**

Pediatric heart failure patients age 6 months to less than 15 years with volume overload despite having received conventional diuretic therapy

“Pediatric heart failure patients with volume overload despite having received conventional diuretic therapy” are defined as patients with volume overload despite

having received any of the following diuretic therapies 1) in whom sufficient effects cannot be expected even if the dose of the diuretics is increased, or 2) in whom the investigator or subinvestigator judges that increasing the dose of the diuretics is difficult due to concerns regarding electrolyte abnormalities or other side effects.

- Furosemide (oral administration)  $\geq 0.5$  mg/kg/day  
(Azosemide 30 mg and torasemide 4 mg will be calculated as equivalent to furosemide 20 mg.)
- Hydrochlorothiazide  $\geq 2$  mg/kg/day
- Trichlormethiazide  $\geq 0.05$  mg/kg/day
- Spironolactone  $\geq 1$  mg/kg/day

### 3.4 Handling of Time Points

Case report form (CRF) Visit values at follow-up period will be used in summaries. Unscheduled Visit values will not be used.

Baseline for each variable is defined as follows.

Table 3.4-1 Handling of Time Points	
Variable	Baseline
Body weight	Before start of IMP administration on the first day of the treatment period
Edema (lower limbs, eyelids, or other sites), jugular venous distension, dyspnea, respiration rate at rest, and pulse rate (edematous symptoms)	Pretreatment observation period (final measurement)
Pulmonary congestion, pleural effusion, and cardiothoracic ratio	Pretreatment observation period
Daily urine volume, daily fluid intake, daily fluid balance, urine osmolality, daily urine sodium excretion, and daily urine potassium excretion	From the day before the start of IMP administration to the first day of the treatment period
Laboratory test values, vital signs, and serum osmolality	The day before the start of IMP administration
Serum or blood sodium concentration and serum or blood potassium concentration (pharmacodynamics)	Before start of IMP administration on the first day of the treatment period
12-lead electrocardiogram	Pretreatment observation period
Plasma arginine vasopressin (AVP) concentration	The day before the start of IMP administration

For serum or blood sodium concentration (laboratory test values and pharmacodynamic endpoint), if the values measured at withdrawal examination are used to summarize the data at each time point, those values will be handled as the values at prebreakfast (however, if the values measured at withdrawal examination are used to summarize the data on the day after the final administration, these values will not be handled as the values at prebreakfast).

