3.7.3 Safety Assessments

3.7.3.1 Adverse Events

Refer to [Section 5](#).

3.7.3.2 **Laboratory tests**

For laboratory tests, each trial site should use appropriate equipment and apparatuses with reliable precision, and follow the procedures specified by the site (measurement at the site). When measurement at the site is not feasible, samples may be sent to the contract research organization for clinical laboratory tests (hereafter, central laboratory) for measurement. The central laboratory will measure the following items according to the procedures specified by the laboratory, and report the result of measurement to the sponsor, and the investigator or subinvestigator. The status (with or without blood/urine sampling), the date and time of blood sampling, the date of urine sampling, and the result of measurement will be recorded in a source document and a CRF. The result of measurement by the specified central laboratory does not have to be recorded.

The case where the subject cannot provide urine sample for some reason despite having received an instruction to urinate will not be regarded as a deviation, but the reason should be recorded in a CRF. To ensure the safety of the subject, a sample should be obtained at a different time or day.

Unscheduled laboratory tests, if required at the occurrence of AEs or for the follow-up of AEs, should be performed at each trial site.

Table 3.7.3.2-1 Clinical Laboratory Assessments

Hematology: Hemoglobin Mean Corpuscular Hemoglobin Concentration Mean Corpuscular Volume Hematocrit Red Blood Cell count White Blood Cell count with differential Platelet count	Serum Chemistry: Alkaline Phosphatase ALT AST Bilirubin, total Blood Urea Nitrogen Uric acid Cholesterol Creatinine Gamma Glutamyl Transpeptidase Glucose Lactic Dehydrogenase Potassium Protein, total Albumin Sodium Triglycerides
Urinalysis: Color Occult blood Glucose pH Protein Specific gravity	Additional Tests: Urine pregnancy test for all female subjects who have begun menstruation

In all female subjects who have begun menstruation, a pregnancy test will be conducted at screening examination, and results must be available prior to tolvaptan administration.

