3.8.3 Individual Subject Discontinuation

3.8.3.1 Treatment Discontinuation

Treatment with the IMP should be discontinued, and the withdrawal examination specified in [Section 3.7.1.6](#) should be performed, in the cases listed below. Each investigator or subinvestigator will comprehensively review the circumstances and record the date and reason of discontinuation in a source document and a CRF.

- 1) Legal representative or subject requests to be withdrawn
- 2) After start of IMP administration, a deviation from the inclusion or exclusion criteria is discovered for the subject
- 3) Continuation of treatment is deemed unfeasible due to the occurrence of AEs
- 4) Any of the prohibited concomitant medications are used
- 5) The dose and regimen of restricted concomitant medication were changed within 24 hours before and after start of IMP administration

- 6) Excessive aquaresis is observed, or dose reduction to ≥ 2 dose steps lower is required due to concerns regarding the safety of the subject
- 7) Liver function test value (AST or ALT) increased by ≥ 3 times the upper limit of the reference range for the subject's age and gender
- 8) Serum or blood sodium concentration increased by ≥ 12 mEq/L from that immediately before IMP administration, within 24 hours after administration
- 9) Serum or blood sodium concentration increased by ≥ 8 mEq/L from that immediately before IMP administration, within 8 to 12 hours after administration
- 10) Serum or blood sodium concentration exceeding 145 mEq/L is observed during the treatment period
- 11) Serum or blood potassium concentration exceeds the upper limit of the reference range for the subject's age and gender during the treatment period
- 12) Subject's pregnancy is confirmed or suspected
- 13) The investigator or subinvestigator judges that withdrawal is necessary for any other reasons

After start of treatment with the IMP, a subject may stop treatment permanently for a variety of reasons. Treatment discontinuations may be initiated by a subject who is not satisfied with treatment, when medically necessary due to AEs, when requiring treatment with a disallowed medication or therapy, or other issues, as determined by the investigator. However, options for continued treatment should be offered to the legal representative or subject to the degree possible as described in [Section 3.8.3.4](#).

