## **5.6 Handling of Missing Data**

If data on body weight and edematous symptoms cannot be obtained for assessment on (the day after) the third day of administration at the evaluation dose, the missing data will be imputed using the last available data obtained by that day.

If data on body weight on the day after the third day of administration at the evaluation dose cannot be obtained for the primary endpoint, the definition of the primary endpoint, “the mean daily urine volume for the 3 days of treatment at the evaluation dose” ([Section 6.1](#)), will be changed to “the mean daily urine volume from the start of administration at the evaluation dose to the day on which the imputed data on body weight is obtained.”

If data on body weight, edematous symptoms, and safety endpoints cannot be obtained even on the day of (or the day after) the final administration at the evaluation dose and the day of (or the day after) the final administration, the missing data will be imputed using the last previous data obtained.

The missing data will be imputed when there are data after the administration at the evaluation dose for (the day after) the third day of administration at the evaluation dose and the day of (or the day after) the final administration at the evaluation dose, or after the IMP administration for the day of (or the day after) the final administration (‘after the administration at the evaluation dose’ for the analysis with baseline as the first day or immediately before the start of administration at the evaluation dose).

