## **9.3 Clinical Laboratory Data**

For clinical laboratory tests other than qualitative urinalysis (except for pH and specific gravity in urinalysis), descriptive statistics of the measured values and changes from baseline at each time point after the start of administration at the evaluation dose and on the day after the final administration will be calculated. For qualitative urinalysis parameters, shift tables at each time point after the start of administration at the evaluation dose and on the day after the final administration compared with baseline will be prepared (except for color). For clinical laboratory test parameters other than qualitative urinalysis, a specified site reference range will be used to classify the measurements into measurements “within the reference range,” “below the reference range,” or “above the reference range,” and shift tables of classifications at each time point after the start of administration at the evaluation dose and on the day after the final administration compared with baseline will be prepared.

An analysis will also be performed using data collected immediately before start of administration at evaluation dose as a baseline. In addition, data will be summarized by the number of days elapsed since start of administration.

For ALP, the value calculated by the IFCC method will be used for the descriptive statistics (for the measured values by the JSCC method, a conversion factor of 0.35 will be used to summarize the converted values).

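### Laboratory summaries may omit unscheduled post-dose sodium and potassium values, and no table counts how many subjects crossed the protocol's sodium stopping limits

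*SAP*

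**What the plan says.** SAP 3.4 (Handling of Time Points) rules that "Unscheduled Visit values will not be used". The sentence just before it is "Case report form (CRF) Visit values at follow-up period will be used in summaries", so the exclusion can be read as general or as limited to follow-up. The same section deals with sodium from the withdrawal examination: "if the values measured at withdrawal examination are used to summarize the data at each time point", they count as prebreakfast values.

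Protocol 3.7.3.2 (Laboratory tests) foresees extra draws: "Unscheduled laboratory tests, if required at the occurrence of AEs or for the follow-up of AEs, should be performed at each trial site".

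SAP 5.6 adds a carry-forward rule that begins "If data on body weight, edematous symptoms, and safety endpoints cannot be obtained even on the day of" (or the day after) final administration, both at the evaluation dose and overall. In that event "the missing data will be imputed using the last previous data obtained". Protocol 7.3 has carry-forward for body weight and edematous symptoms only. SAP 14 mentions Protocol 7.3, but only for the timing of symptom assessments.

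For shift tables, SAP 9.3 says that "a specified site reference range will be used to classify the measurements" as within, below or above range. Protocol 3.8.3.1 requires treatment to stop when "Serum or blood sodium concentration exceeding 145 mEq/L is observed during the treatment period". It also requires this when sodium rises by at least 8 mEq/L within 8 to 12 hours or at least 12 mEq/L within 24 hours of the value immediately before administration, or when potassium exceeds the upper reference limit for age and gender.

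**The concern.** Safety is part of the primary objective, and the rationale for inclusion criterion 3 (Protocol 3.4.2) names a rapid rise in sodium as the hazard to be managed. Unscheduled draws are taken because something seems wrong, so they are where an abnormal value is likely to be found. If the summaries leave them out, and an earlier value can stand in at the final-administration time points, the laboratory tables may understate the worst values.

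The protocol also defines exact sodium limits that end treatment, yet the SAP plans no count of subjects who reached each one. It does plan such counts for QTc (SAP 9.5: above 450, 480 and 500 msec). A reader of the results would want the equivalent for sodium, with a denominator.

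**Working it through.** The plan states no figure on this point, so there is none to reproduce. The check compares the draw schedule, the SAP rules and the table list.

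**1. Scheduled post-dose sodium.** Protocol 3.7.1.3.1 has draws at 4 to 6 and 8 to 12 hours on Day 1. The schedules for Days 3, 5 and 7 repeat them only when the dose is increased that day. Days 2, 4, 6, 8 and 9, the extension days (3.7.1.4) and the reduced-dose days (3.7.1.5) have a predose draw only. Without dose reduction:

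| Dose decided (mg/kg/day) | Dosing days | Days with scheduled same-day post-dose sodium | With 4-day extension |
|---|---|---|---|
| 0.05 | 3 | 1 (Day 1) | 1 of 7 |
| 0.15 | 2+3 = 5 | 2 (Days 1, 3) | 2 of 9 |
| 0.3 | 4+3 = 7 | 3 (Days 1, 3, 5) | 3 of 11 |
| 0.5 | 6+3 = 9 | 4 (Days 1, 3, 5, 7) | 4 of 13 |

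The next morning's predose draw falls about 24 hours after each dose and is scheduled throughout. What is missing on the other days is the interval between. Scheduled potassium on every dosing day is before breakfast only.

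**2. Where a same-day post-dose value would come from on the other days.** Only from an unscheduled draw or the withdrawal examination. Protocol 3.7.1.6 includes both electrolytes in that examination, but a test already done on the day of discontinuation need not be repeated. The draw that prompted the stop may then be the only value. The SAP does not say whether it counts as unscheduled.

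**3. Carry-forward.** In that case the value after final administration could be missing, and SAP 5.6 would supply a previous one, possibly from before the peak. The rule does not say whether an unscheduled result may serve as that value.

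**4. What the planned tables show for each limit.**

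- *Sodium above 145 mEq/L:* descriptive statistics by time point include the maximum, which shows whether any scheduled value exceeded 145 but not in how many subjects. The shift tables (CT-10.4.1 to 10.4.3) use site ranges, whose upper limits need not be 145.
- *The two rise limits:* the reference is the value immediately before administration. SAP baselines are the day before treatment (laboratory values), Day 1 predose (pharmacodynamic sodium), or just before the evaluation dose. The Day 1 and evaluation-dose baselines match the protocol reference on the first day of those doses. For an evaluation dose of 0.5 mg/kg/day, the rises on starting 0.15 (Day 3) and 0.3 (Day 5) are not derived. For an evaluation dose of 0.3, the rise on starting 0.15 is not.
- *Potassium:* above range is counted by time point in CT-10.4.1 to 10.4.3. There is no any-time count per subject, and the SAP does not say that the site range is specific to age and gender.

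**5. What a count would deliver.** With x of n = 60 planned subjects, the exact limits are the 2.5% point of Beta(x, n−x+1) and the 97.5% point of Beta(x+1, n−x). For assumed counts, 1/60 = 1.7% (0.0 to 8.9) and 2/60 = 3.3% (0.4 to 11.5). One subject more or less visibly moves the upper limit, so completeness of capture matters at this sample size.

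**The case against.** Much can be said for the plan. Sodium is drawn before every dose and twice after the doses that start or raise treatment, when the 8-to-12-hour limit has a matching draw. These values enter the summaries with minimum and maximum, and withdrawal-examination sodium can too. A laboratory value that leads to discontinuation is by definition an adverse event (Protocol 5.1), whatever kind of draw produced it. It then appears in the tables of treatment-emergent events leading to discontinuation (CT-9.1.5, with versions by age and evaluation dose). Subjects who met a withdrawal criterion and stayed on treatment fall into a serious-deviation category (SAP 7.6). Carry-forward of safety values applies only at the final-administration time points, and only if data are missing there.

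All of this stands. It rules out the stronger inferences that unscheduled peaks would vanish from all output, that no stopping limit is tabulated in any form, or that safety data are carried forward generally. It does not close the gap. The event tables go by preferred term, not by criterion, and the deviation category pools all criteria. CT-10.5, LAB-1 and PDATA-9 are listings, and the SAP does not say whether they include unscheduled values.

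The exclusion in SAP 3.4 may concern follow-up only. On that reading the SAP has no stated rule for unscheduled values during treatment and still needs one.

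**Conclusion.** The point holds as a partial gap. Post-dose peaks on days without a dose increase may not reach the laboratory tables. The three sodium limits have no per-subject, any-time count, and the protocol's rise from the predose value is not derived at intermediate dose steps. Carry-forward for safety endpoints is an unlisted departure from Protocol 7.3.

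The structural size is known: 2 of 3 dosing days (stay at 0.05 mg/kg/day) to 5 of 9 (titration to 0.5) lack a scheduled same-day post-dose sodium, before any extension. The number of subjects affected is not, because the documents give no rate of unscheduled draws. It would be wrong to conclude that the plan produces a false incidence for these limits, since it produces none.

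The verdict assumes that the exclusion in SAP 3.4 reaches the treatment period and that "immediately before" administration in the rise limits means that day's predose value.

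**What to change.** 1. Keep scheduled-only values for the by-visit summaries. Add one table, labelled worst-value, using all post-dose results: scheduled, unscheduled and withdrawal examination. Give the number, percentage and exact 95% confidence interval of subjects meeting each sodium and potassium limit already written in Protocol 3.8.3.1. Use the same-day predose value as reference for the rise limits. Present it overall, by age group and by dose at the time.
2. In SAP 5.6, drop carry-forward for safety endpoints or let it use the last observed value of any kind, and list the change in SAP 14.
3. In SAP 3.4, state which period the exclusion covers, and say whether the listings include unscheduled values.

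The cost is a few SAP sentences and one table. It needs no new data, provided unscheduled results are recorded like scheduled ones, and no new clinical rule. The drawback is that sicker subjects have more unscheduled draws and so more chances to show an extreme value. The table must be read as worst-value, with caution when comparing ages or doses.

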3.7.1.3.1 Day 1 of Treatment Period

The investigator or subinvestigator will perform the following procedures.

1) Before tolvaptan administration

The investigator or subinvestigator will perform the following examinations, and then, offer breakfast to the subject.

- Body weight
- Serum or blood sodium concentration
- Serum or blood potassium concentration

The investigator or subinvestigator will instruct the subject to completely discharge the urine immediately after breakfast, and start urine collection and fluid intake measurement to assess the following items.

- Daily urine volume
- Daily fluid intake

- Daily fluid balance
- Urine sodium excretion
- Urine potassium excretion
- Urine osmolality

2) Tolvaptan administration

The investigator or subinvestigator will instruct the subject to take tolvaptan (0.05 mg/kg/day) with water after breakfast. After administration, the change in serum or blood sodium concentration will be observed. If the change meets the following criteria, the investigator or subinvestigator should discontinue treatment with tolvaptan as specified in [Section 3.8.3.1](#), and perform the withdrawal examination according to [Section 3.7.1.6](#).

- Serum or blood sodium concentration increased by ≥ 8 mEq/L from that immediately before tolvaptan administration, within 8 to 12 hours after administration
- Serum or blood sodium concentration increased by ≥ 12 mEq/L from that immediately before tolvaptan administration, within 24 hours after administration
- Serum or blood sodium concentration exceeding 145 mEq/L is observed during the treatment period

3) 4 to 6 hours after tolvaptan administration

- Serum or blood sodium concentration

4) 8 to 12 hours after tolvaptan administration

- Serum or blood sodium concentration

5) At a feasible time

- Vital signs
- Edematous symptoms (after tolvaptan administration)
- Concomitant drugs and therapies
- IMP compliance
- Adverse events

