3.7.4.2.4 Serum or Blood Sodium Concentration

For laboratory tests, each trial site should use appropriate equipment and apparatuses with reliable precision, and follow the procedures specified by the site (measurement at the site). When measurement at the site is not feasible, samples may be sent to the specified central laboratory for measurement. In that case, however, the same measurement procedure should be followed for each subject. The status (collected/not collected), and date and time of blood sampling, as well as the result of measurement will be recorded in a source document and a CRF. The result of measurement by the specified central laboratory does not have to be recorded.

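### Sodium taken at the withdrawal examination is labelled pre-breakfast whatever the time it was drawn, so a post-dose value can be counted in a predose row

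*SAP*

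**What the plan says.** The rule is in SAP 3.4, after the table of baselines. It covers sodium both as a laboratory value and as a pharmacodynamic endpoint, and it has three parts:

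- a condition: "if the values measured at withdrawal examination are used to summarize the data at each time point";
- the label that then applies: "those values will be handled as the values at prebreakfast";
- an exception for the day after final administration, where "these values will not be handled as the values at prebreakfast".

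The label does not depend on the sampling time. The same section also says "Unscheduled Visit values will not be used". I find no sentence in the SAP that says when the condition is met.

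Protocol 3.8.3.1 lists 13 reasons for stopping treatment, each followed by the withdrawal examination of Protocol 3.7.1.6. Three concern sodium. One is a rise of at least 8 mEq/L "from that immediately before IMP administration, within 8 to 12 hours after administration", one is a rise of at least 12 mEq/L within 24 hours, and one reads "Serum or blood sodium concentration exceeding 145 mEq/L is observed during the treatment period".

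For sodium samples, Protocol 3.7.4.2.4 requires: "The status (collected/not collected), and date and time of blood sampling, as well as the result of measurement will be recorded".

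**The concern.** In the treatment-day schedules (Protocol 3.7.1.3.1 to 3.7.1.3.9, 3.7.1.4.1 to 3.7.1.4.4 and 3.7.1.5.1 to 3.7.1.5.4), the morning sodium is drawn first, then breakfast is given, then the dose. A pre-breakfast row on a treatment day is therefore a predose row. Labelling a sample drawn hours after the dose as pre-breakfast gives it a time point it does not have.

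The misplacement is not random. It can arise only in subjects who stopped treatment, and some of them stopped because sodium rose after the dose. Sodium is both a safety and a pharmacodynamic variable here. The pharmacodynamic tables are split by age group, by evaluation dose and by both, so some cells will be small. In the shift tables, a post-dose value above the reference range could appear as an abnormal predose value.

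**Working it through.** The plan gives no figure for this point, so there is none to reproduce. The check sets the passages side by side and then sizes the possible effect under stated assumptions.

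**Step 1. When sodium is drawn**

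| Occasion | Time of sodium sample | Source |
|---|---|---|
| Every treatment day | Before breakfast and dose | Protocol 3.7.1.3 to 3.7.1.5 |
| Day 1 | Also 4–6 h and 8–12 h after dose | Protocol 3.7.1.3.1 |
| Days 3, 5 and 7, if the dose is increased | Also 4–6 h and 8–12 h after dose | Protocol 3.7.1.3.3, 3.7.1.3.5, 3.7.1.3.7 |
| Withdrawal examination | No clock time and no time since dose | Protocol 3.7.1.6 |

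Under Protocol 3.7.1.6, a test already done on the day of discontinuation need not be repeated.

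**Step 2. Following one subject**

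Suppose a subject meets the Day 1 criterion: "Serum or blood sodium concentration increased by ≥ 8 mEq/L from that immediately before tolvaptan administration, within 8 to 12 hours after administration". That finding is post-dose by definition, and the withdrawal examination follows.

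- *A separate withdrawal sample is drawn that evening.* Its true time is post-dose, but if it enters a by-time-point summary SAP 3.4 makes it a pre-breakfast value. The subject already has a scheduled pre-breakfast sodium for Day 1. The SAP does not say whether the withdrawal value replaces it, stands beside it or moves to another day.
- *The 8–12 h sample is not repeated and also serves as the withdrawal sample.* The documents do not say which label it then carries.

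Now suppose instead that a 24-hour rise is found at the next morning's draw before breakfast. There the pre-breakfast label is correct.

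So the rule can be right or wrong for a given subject, and only the recorded sampling time tells which.

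**Step 3. Where the value would appear**

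Because the rule names both uses of sodium, it reaches the descriptive tables PDT-2.x (overall, by age, by evaluation dose and by both) and the sodium and potassium shift tables CT-10.4.x.

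**Step 4. Size, under assumptions**

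Let k of the n values in a row each be replaced by a value d mEq/L above the subject's true predose value. Then

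shift in row mean = k × d / n.

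Take k = 1 and d = 8 to 12, the two rise limits in Protocol 3.8.3.1. The planned total is n = 60. The smaller cells are assumed even splits: 60/4 doses = 15, and 60/(4 doses × 3 age groups) = 5.

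| n | 1 × 8 / n | 1 × 12 / n |
|---|---|---|
| 60 | 0.13 | 0.20 |
| 15 (assumed) | 0.53 | 0.80 |
| 5 (assumed) | 1.6 | 2.4 |

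With wider inputs (k = 1 to 4, d = 4 to 12), n = 60 gives 1 × 4/60 = 0.07 to 4 × 12/60 = 0.80 mEq/L. An assumed n = 20 gives 1 × 4/20 = 0.20 to 4 × 12/20 = 2.40 mEq/L.

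**The case against.** The best defence is that the rule is narrow and hides nothing. It applies only if withdrawal values are used by time point, and it exempts the day after final administration. Only three of the 13 stopping reasons concern sodium. On days without a first dose or a dose increase, the only scheduled sodium is the morning one, so a value above 145 mEq/L found then may truly be predose, and that criterion sets no minimum rise. The withdrawal sample may also be later than the triggering one, so it need not be 8–12 mEq/L up. Evidence for each subject survives elsewhere. A laboratory value that leads to discontinuation is an adverse event (Protocol 5.1) and is reported in CT-9.1.5 and CT-9.9. Abnormal results are in CT-10.5, and individual sodium values are in PDATA-9. In the affected row the error raises sodium, so it does not understate hypernatraemia there.

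All of this stands, and it keeps the point small. It does not make the label right for a sample drawn after the dose. The exception does not help on treatment days, which is where pre-breakfast means predose.

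A reader might go further and infer that the rule removes post-dose peaks from the post-dose rows. The documents do not support that. SAP 3.4 speaks only of values measured at the withdrawal examination, and the 4–6 h and 8–12 h samples are separate scheduled measurements that keep their time points. One could be lost only if it were recorded solely as the withdrawal sample, and the documents do not say how that is handled. On days with no scheduled post-dose sample there is no such row to deplete.

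**Conclusion.** The point holds as a minor one. SAP 3.4 states a rule that can place a post-dose sodium value in a predose row. The bias in that row is upward when the value is a post-dose rise; for other withdrawals the direction is not determined.

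The illustrated size is 0.13–0.20 mEq/L for one value among 60. It grows to 0.5–0.8 and 1.6–2.4 mEq/L in cells of 15 and 5. These figures assume that the withdrawal value is 8–12 mEq/L above the subject's true predose value and replaces it. The SAP does not state that replacement, and the cell sizes are even splits of 60, which dose titration to response gives no reason to expect. The number of subjects affected cannot be known from the documents. The primary endpoint is not touched.

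**What to change.** Replace the sentence in SAP 3.4 with a rule based on the recorded sampling time:

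- Treat withdrawal-examination sodium as pre-breakfast only if it was drawn before breakfast and before that day's dose.
- Otherwise show it in a separate 'withdrawal' row of the sodium tables and in the existing listings, CT-10.5 (for abnormal values) and PDATA-9.
- State that a scheduled post-dose sample that also serves as the withdrawal sample keeps its nominal time point.
- State that a withdrawal value never replaces an existing pre-breakfast value from the same day.

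A separate row is better than moving every such value into the 4–6 h or 8–12 h window. Those windows are scheduled only on Day 1 and on dose-increase days. On other days the move would create post-dose rows made up solely of subjects who stopped, and on scheduled days it could duplicate an existing value.

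The cost is a short SAP edit, a small programming change and one extra, sparse table row. No new data are needed, because sampling times are already collected. The SAP already uses actual sampling times for its pharmacokinetic figure (SAP 10).
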